4.2.2 Secondary Outcome Measures

Secondary outcome measures for this study include the effect of lacosamide on 1) cognitive

function, and 2) alcohol use and craving during the titration period. The Controlled Word Association (COWAT)⁴⁰ and the Wechsler Adult Intelligence Scale (WAIS-5)⁴¹ Spatial and Digit Span tests will be used to assess the effects of lacosamide administration on cognitive function. The Obsessive-Compulsive Drinking Scale (OCDS)⁴², and the alcohol VAS will be used to assess the effects of lacosamide on craving during the medication titration period.

5 Study Design

This is a double-blind, randomized, placebo-controlled, crossover design trial that will test the effect of lacosamide on alcohol self-administration and craving following a priming dose of alcohol. An established human laboratory self-administration procedure will be followed³⁸. The O'Malley self-administration procedure entails the administration of a priming drink followed by the presentation of four drinks on a tray which subjects may drink, or receive compensation for the drinks not consumed. After one hour the first tray of drinks is removed and subjects are then given the opportunity to consume a second tray of drinks. Confirmation of the validity of this approach as a method for screening for medications to treat AUD include the finding that pretreatment with naltrexone, which is an approved medication for treating AUD, significantly reduced alcohol consumption when the O'Malley self-administration procedure was used⁴⁵. Using this procedure, our group has found that the anticonvulsant zonisamide reduces alcohol consumption in non-treatment seeking social drinkers⁴³. We later confirmed that the administration of zonisamide decreases alcohol consumption in subjects with AUD in a doubleblind randomized clinical trial²⁵ as have other investigators⁴³. Testing lacosamide using O'Malley's self-administration procedure is the next logical step in drug development following positive findings that lacosamide reduces drinking in animal models. The human laboratorybased alcohol self-administration procedure is a cost effective and time-efficient method for testing novel drug candidates for AUD treatment⁶.

Subjects: Heavy-drinking subjects will be enrolled to increase the potential generalizability of these findings to a clinical AUD population. Subjects will be recruited through radio advertisements, newspaper advertisements, internet advertisements, study flyers, internet postings, and an established subject registry at Boston Medical Center. Interested subjects will be screened by telephone to determine initial eligibility prior to the baseline assessment.

6 Potential Risks and Benefits

6.1 Risks

Risks of study medication (see product insert)

To minimize the risk of adverse health events we will instruct subjects to contact study staff with any questions or concerns about changes in health effects after initiating study medication/placebo. Trained medical staff will evaluate any reported adverse effects and make a clinical determination about management through dosing methods (e.g., taking before bedtime or with food), dose discontinuation, and/or referral for medical care. Subjects will be given a wallet card that includes a phone number with 24/7 coverage for medical emergencies. As an added

safety precaution, subjects will be contacted mid-week of the titration period for an adverse effect assessment.

Adverse effects

Treatment emergent adverse events (TEAs) in studies of the effects of lacosamide are shown in the three tables below. Of most relevance to this protocol are findings from the TEAs in healthy subjects shown in Table 1. The least tolerated dose reported for healthy subjects was found in a study that subjects that received 400 mg per day of lacosamide for 6 days without a period of drug titration⁴⁴. Roughly 8% of subjects in this study reported feeling drunk at this dose.

Table 1. Common TE.	As for healthy subjects	obtained in 3 studies
TEA	Healthy $(n=20)^{45}$	Healthy $(n=50)^{46}$

TEA	Healthy (n=20) ⁴⁵	Healthy (n=50) ⁴⁶	Healthy (n=56) ⁴⁴	Healthy (n=54) ⁴⁴
	300mg	300 mg	400 mg	Placebo
	6 Weeks	21 Days	6 days	6 days
	3 Week Titration	3 Week Titration	No Titration	No Titration
Dizziness	2%	7.4%	10.0%	6.5%
Somnolence	4.0%	11.1%	Not Reported	Not reported
Headache	10.0%	11.1%	16.7%	14.5%
Nausea	4.0%	Not reported	8.3%	1.6%

Data from seizure patients who received lacosamide as monotherapy is presented in Table 2⁴⁷. At the 300 mg dose these patients showed a greater incidence of dizziness, nausea, and headache than did healthy subjects treated with this dose. Data from the monotherapy study also includes findings from when subjects were also receiving other anticonvulsant medications.

Table 2. Findings for lacosamide monotherapy studies.

TEA	Monotherapy ⁴⁷	Monotherapy	Monotherapy Newly
			Diagnosed Subjects ⁴⁸
	300mg	400 mg	200-400 mg/day
	N=106	N=319	N=444
Dizziness	17.9	26.0	12%
Somnolence	14.2	9.1	5%
Headache	17.9	13.2	14%
Nausea	12.3	13.8	6%
Blurred	5.7	6	Not reported
Vision			

Table 3 includes data from seizure patients treated with lacosamide in combination with other anticonvulsant drugs during the titration phase for lacosamide.

Table 3. Pooled percent common TEAs for focal seizure patients treated with lacosamide as an adjunctive medication obtained for the titration phase of 3 RCT's. 49

TEA	200 mg (n=270)	400 mg (n=471)	Placebo (n=364)
Dizziness	10.4	24.6	6.6
Fatigue	6.7	6.8	5.2
Ataxia	2.2	5.9	1.4
Balance Disorder	0.7	3.6	0.0
Nausea	5.6	8.5	3.6
Blurred Vision	1.9	6.2	1.6
Diplopla	4.4	8.3	1.1

Risks of Dizziness. Ataxia, Somnolence, and Incoordination

Data presented in the tables shown above suggest that there may an increased risk of dizziness, ataxia, somnolence, and incoordination associated with the administration of lacosamide to healthy subjects. Consequently, subjects in this study will be counseled that the administration of lacosamide may produce dizziness, double vision, somnolence, and problems with balance and coordination. They be advised to avoid driving, operating complex machinery, or engaging in other hazardous activities until they have become familiar with the effects of lacosamide.

Physical discomforts:

The drawing of blood may cause pain, bruising, lightheadedness, and on rare occasions, infection. Subjects may briefly feel the prick of the needle when it is inserted. Subjects may feel dizzy or faint when blood is drawn. Trained phlebotomists will be used to minimize these risks.

ECGs may cause discomfort and/or irritation of the skin (redness and itching) from the adhesive electrodes. Hair on your chest may need to be removed in order to obtain the best electrical contact between the adhesive electrodes and subjects' skin. Trained staff will be used to minimize these risks.

Cardiac Risks

A dose dependent prolongation of the PR interval has been observed in both patients and healthy subjects who have received lacosamide. Asymptomatic atrioventricular (AV) block has been observed in clinical trials in 0.4% of patients being treated for seizures and 0.5% of patients being treated for diabetic neuropathy. Cases of second degree and complete atrioventricular block have been seen in both seizure and pain patients. In two postmarketing reports, third degree AV block was observed in patients who had a significant cardiac history and were being treated the beta blocking drug metoprolol and the calcium channel blocker amlodipine when receiving infusions of lacosamide at above the recommended doses for this drug. Bradycardia also has been observed in patients who have received intravenous infusions of lacosamide.

No cases of atrial fibrillation or flutter were observed in the short-term investigational trials of lacosamide seizure patients. Cases of atrial fibrillation and atrial flutter, however, have been detected in both open label epilepsy trials and in postmarketing experience. In patients who had diabetic neuropathy, 0.5% of patients had episodes of atrial fibrillation or atrial flutter while no episodes of these disorders occurred in placebo-treated patients.

It is recommended that lacosamide be used with caution in patients with previously identified conduction problems including marked first-degree AV block, second-degree or higher AV

block and sick sinus syndrome without pacemaker), sodium channelopathies, a history of myocardial infarction or congestive heart failure. Its use should be avoided in individuals who are receiving other medications that may prolong the PR interval.

To minimize the risk of cardiac adverse events, the published caution guidelines will be used to exclude patients from entering this study. All study candidates will receive an ECG to detect disturbances in cardiac function that may place them at risk for a cardiac conduction problem if they were to receive lacosamide. Patients will be excluded if either the results of the ECG recording or their medical history indicates that they would be at risk of developing cardiac problems from lacosamide use. Study candidates will also be excluded from study entry if they are taking any medication that may block cardiac conduction. This will include the use of any antiarrhymic agents including beta and calcium channels blockers and digoxin.

Psychiatric risks

In clinical trials of the effects of antiepileptic drugs (AED), the incidence of suicidal behavior or ideation was 0.43% in AED-treated-subjects versus 0.24% for placebo-treated patients, representing an increase of approximately 1 case of suicidal thinking or behavior for every 530 treated patients. These trials included 27,863 patients being with AED and 16,029 patients to who placebo was administered. There were four suicides in drug-treated patients in these trials and none in the placebo-treated patients. Because of these finding treatment with any anticonvulsant medication including lacosamide must be considered to produce to an increased risk of suicidal thoughts and behaviors.

To minimize the risk of worsening suicidal thoughts and behaviors we will screen for suicidality using the Columbia-Suicide Severity Rating Scale and the MINI Neuropsychiatric Interview. Subjects with a MINI suicidality score greater than 8 (low risk) will be excluded. Subjects who report any active suicidal thoughts or behavior as measured the C-SSRS will be excluded from participation. In addition to excluding active suicidality, the MINI will be used to rule out subjects who have psychiatric conditions that may increase the risk of the occurrence of suicidal thoughts or behavior (e.g., major depression, bipolar disorder). Assessment and scoring of suicide rating scales will be conducted in real-time while the subject is present. Suicidality will be assessed by trained clinical staff including study MDs, a psychologist, a nurse, and a mental health counselor. If subjects are found to be at risk for self harm, study staff will work with the subject to develop a safety plan that could include escorting the subject to the BMC ED or calling BEST. To minimize the risk of abuse of lacosamide, subjects with lifetime substance use disorders will be excluded (with the exception of marijuana, caffeine, nicotine and alcohol). To date, there are no published reports of the abuse of lacosamide.

Risk to a developing fetus

The administration of lacosamide to pregnant rats has been found to produced developmental toxicity that included increased embryofetal and perinatal mortality, and growth deficits. following administration during pregnancy. Neurotoxicity has been seen in rats who received this drug during a period of postnatal development believe to correspond to the third trimester of human pregnancy.

To protect against the risk of potential developmental toxicity to a fetus, women will be excluded from study entry if they have a positive urine pregnancy test or if they are of childbearing age and are either not using appropriate methods of contraception or not practicing abstinence. Urine

pregnancy testing will also be completed at each study visit as a protection to the developing fetus. Subjects with positive pregnancy test results will be discontinued form participation

Risk of Drug Reaction with Eosinophilia and Systemic Symptoms (DRESS)/Multi-Organ Hypersensitivity

During the clinical development of lacosamide one case of symptomatic hepatitis and nephritis was observed among 4011 subjects exposed to this drug. This happened in a healthy volunteer, 10 days after the discontinuation of lacosamide. This case was deemed to be consistent with a delayed multi-organ hypersensitivity reaction. Other possible cases included two subjects who had a rash and elevated liver enzymes and one subject who had myocarditis and hepatitis of uncertain etiology. We ask that subjects contact a study physician immediately if they develop a rash, fever, become excessively tired, notice that their urine turns brown, or notice your skin turning yellow.

Risk of Stevens Johnson Syndrome /Toxic Epidermal Necrolysis

Post-marketing data indicate the occurrence of cases of Stevens Johnson Syndrome and Toxic Epidermal Necrolysis in patients being treated with lacosamide. This data does not allow for determination of a reliable estimate of frequency of occurrence these disorders being treated with lacosamide nor do they establish a causal relationship between appearance of these disorders and exposure to this anticonvulsant. Subjects will be asked to contact a study physician immediately if they develop a rash, fever, sore throat, mouth ulcers, or bruising while taking the study medication.

Risks of alcohol self-administration

Risk to recovery efforts

Treatment-seeking drinkers will be excluded from this study to minimize the risk that drinking in the laboratory could worsen outcomes for a subject trying to reduce or abstain from alcohol. All subjects will undergo a medical screening and we will exclude subjects who have a medical or mental condition for which alcohol exposure in this study would be contraindicated. All subjects will receive the NIAAA self-help guide *Rethinking Drinking* at the end of study participation.

Risk of overconsumption

To minimize the risk of subjects reaching a level of intoxication that is uncomfortable to them, we will remind subjects that they may discontinue study participation at any time. Subjects will be asked to drink to a target BAL (.03 g/dl) that is customary for them given the minimum drinking criteria. The alcohol self-administration paradigm that we have chosen does not include any coercion, inducements, or pressure to consume more alcohol than subjects feel comfortable consuming. There are no experimental manipulations that would increase drinking (e.g., heavy drinking confederate, anxiety manipulation). In fact, in this study design there are inducements for subjects to not drink beyond the initial priming dose. Subjects will receive monetary incentives for each drink that they do not consume. Access to medical backup services will be maintained throughout each alcohol challenge session. Subjects will be monitored during the course of the study, both through direct assessment with study staff and by observation through a video camera. Medical staff will evaluate subjects and may make a determination to halt study

participation if the subject becomes too behaviorally impaired or if there are emergent safety issues. Subjects who have a BAL greater than .04 g/dl or who appear to be too behaviorally impaired to leave our research center will be asked to remain in the clinic until their intoxication is reduced to a level that it is safe to discharge them from the research laboratory. BAL readings will be taken twice to confirm BAL is not greater than .04 g/dl prior to release. Subjects will not be released within 60 minutes of their last drink consumed to ensure that peak BAC has been reached prior to discharge. During the descending BAL period, subjects will have access to a comfortable space with entertainment (streaming media), snacks, non-alcoholic beverages, and a nearby bathroom.

Risk of loss of confidentiality

There is some risk that health information collected as part of this study could be seen by unauthorized individuals. Every effort will be made to minimize this risk and protect subject confidentiality. Electronic data will be housed in the REDCap data management system. REDCap is protected via Secure Sockets Layer (SSL) encryption that provides access restriction options. Exported data from REDCap will be stored on a secure password-protected server behind the BMC firewall. Source and CRF binders will be stored in a double-locked area that is accessible to only study staff. Subjects will be assigned a study identification number and this will be used to code any forms that do not require the subject's direct identifiers (e.g., consent form, laboratory results, and contact information). A linking key that associates study ID with direct identifiers will be stored in a double-locked cabinet accessible only by study team members. Data will be stored on a password-protected computer accessible only to the study team. Video of subjects during the drinking session will be stored on an encrypted drive with password protection. Video files will be deleted at the end of the study. All study staff will receive appropriate training for the protection of human subjects (NIH Protecting Human Research Participants, CITI Training). A certificate of confidentiality will be sought to protect subjects from disclosure under court order or subpoena.

6.2 Potential Benefits

There is no potential direct benefit to participation in this study. This study presents a very strong potential for benefit to science. Drug development for treating AUD is costly and few pharmaceutical companies are testing novel compounds as agents to treat AUD. Re-purposing compounds with FDA approval for other indications is the most promising route for rapid and cost-effective development of medications to treat AUD. This study will bridge the gap in drug development by providing a test of lacosamide to see if it may be a candidate drug for treating AUD. If successful, this could lead to the expansion of pharmacotherapy options to treat AUD and a broadening of our understanding of the mechanistic approach to treating AUD.

6.3 Analysis of Risks in Relation to Benefits

Given that lacosamide has FDA approval for another indication and is well-tolerated in other populations, the risk of this medication to human subjects has been established through pre- and post-marketing data. With the protections we have in place for all the potential risks in this study, we believe the risks of this study are well minimized. The study holds significant promise for

informing new models of care given the novel mechanism of lacosamide. We believe the risk/benefit ratio is favorable.

7 Study Subject Selection

7.1 Subject Inclusion Criteria

In order to be eligible to participate in this study, an individual must meet all of the following inclusion criteria:

- 1. 21-55 years of age
- 2. Can provide proof of age with state-issued or federal picture ID
- 3. Exceeds safe weekly drinking limits (\geq 14 drinks for women or \geq 21 drinks for men per week)
- 4. Reports at least an average of one episode per week of binge drinking (>3 for women, >4 in the four weeks prior to baseline screening
- 5. Meets DSM-5 criteria for mild alcohol use disorder or greater severity.
- 6. Have a smartphone to complete some of the study assessments.

7.2 Subject Exclusion Criteria

An individual who meets any of the following criteria will be excluded from participation in this study:

- 1. Currently seeking treatment for alcohol problems
- 2. Clinical Institute Withdrawal Assessment at >10
- 3. DSM-5 diagnosis of current major depression, bipolar disorder, schizophrenia, bulimia/anorexia, dementia, or a substance use disorder other than alcohol, nicotine, marijuana or caffeine
- 4. If female, pregnant, nursing, or have plans to become pregnant
- 5. If female, does not agree to use an accepted form of birth control
- 6. Is currently using medications for which alcohol is a contraindication
- 7. Has a medical or mental health condition for which further alcohol exposure at the planned dose range would be contraindicated.
- 8. Current risk of suicidality (MINI suicidality score greater than 8 (low risk) or Yes to the ideation question #4 of the C-SSRS)
- 9. Has a history of myocardial infarction, congestive heart failure, has a risk for the development of heart block, or are taking medications that can decrease conduction through the atrial ventricular node.
- 11. Has previous exposure to lacosamide
- 12. Has received any form of counseling, self-help, pharmacotherapy, or other intervention to treat AUD in the past 90 days.
- 13. Is unwilling to suspend use of multivitamins that contain riboflavin during study participation
- 14. Has urine toxicology results positive for cocaine, opioids, amphetamines, buprenorphine, methadone, or methamphetamines
- 15. Liver function values AST or ALT are twice the normal limit
- 16. GFR <80 mL/min
- 17. Unable to comfortably abstain from nicotine for a period of 8 hours.

8 Study Intervention

Study Medication

Study medication will be purchased and packaged by the BMC Investigational Pharmacy Service. Lacosamide (100mg and 150mg tablets) will be over-encapsulated with 50mg of riboflavin which will serve as a tracer of medication compliance. Matching placebo will also be packaged using lactose and 50mg of riboflavin. Medication will be dispensed to each subject in two bottles: 1) 11 pills of Lacosamide (100mg) or placebo 2) 3 pills of lacosamide 150mg or placebo. Capsule size required will be determined by IPS with the goal of a minimum capsule size needed for over-encapsulation. If a subject reports losing (or destroying) study medication, a replacement prescription will be written by one of the study physicians and the BMC Investigational Pharmacy will dispense additional medication to replace the lost (or destroyed) medicine.

Dosing

Subjects will take a single 100mg capsule in the evening of randomization day. Subjects will take 100 mg of lacosamide (or placebo) twice per day from day 2 through day 6. On day 7 subjects will increase to 150mg twice daily. Based on the metabolism of this drug, we expect to be within range of 90% of steady state for a 300 mg daily lacosamide dose by day 8 when the alcohol challenge trial will occur which is consistent with the clinical dose range (300-400mg daily as monotherapy) of this drug when it is used for seizure disorders⁵⁵. Subjects who are unable to tolerate the titration period will be discontinued from the study.

								Self-
Dose	Day 1	Day 2	Day 3	Day 4	Day 5	Day 6	Day 7	Admin
AM		100mg	100mg	100mg	100mg	100mg	150mg	150mg
PM	100mg	100mg	100mg	100mg	100mg	100mg	150mg	

Medication Storage

Medication will be stored in the Investigational Pharmacy at room temperature (within the range of 59°F to 86°F) in a secured area until the time that medication is needed for study subjects. Stability and expiry will be monitored by IPS according to the labelling of the medication from the manufacturer.

Medication Labeling

The study number will be preprinted on each bottle label. The label will include the drug name (e.g., Lacosamide XXXmg or placebo"). The label will also have a randomization number, the number of tablets contained in the bottle, storage conditions, the 24/7 phone number of the clinical site, and places to record the subject number and the date dispensed. Additional fields may be added to this label to meet any regulatory requirements as determined by IPS.

Medication Blinding and Unblinding

Study medication and placebo capsules will be identically matched in appearance and the bottle labels will not reveal the drug identity. The Study PI and study physician(s) will make the decision to un-blind the identity of the study medication in the event that the study blind needs to

be broken to make medical decisions regarding subject treatment.

Medication accountability

The site principal investigator (PI) or designated study personnel will maintain a log of all study medication and record of dispensing of all medication to the subject. The site PI or his staff will count the tablets remaining at the end of the study and record the tablet count on the appropriate drug accountability form. Subject compliance with study medication will be assessed by comparing unused capsule count to dispensing logs and dosing records (number of tablets dispensed, number of tablets prescribed, versus the number returned). Subjects will also be asked to account for any missing tablets. If the bottle is not returned, the subject will be asked to report daily drug self-administration.

9 Study Procedures

Study Overview: Each subject will complete 5 clinic visits over a period of up to 44 days of participation. Study participation is comprised of a baseline assessment, randomization visit, alcohol self administration Trial 1, an assessment visit to verify continued eligibility and dispense medication, and a second alcohol self-administration Trial (see figure 1 for an overview of study participation).

Baseline assessment: Consenting subjects will undergo a general medical screen, physical examination, and electrocardiogram. Drinking will be assessed using the TLFB⁵⁰, alcohol withdrawal using the Clinical Institute Withdrawal Assessment⁵¹, and suicidality using the Columbia-Suicide Severity Rating Scale (C-SSRS)⁵². Exclusionary mental health conditions will be assessed using the MINI Neuropsychiatric Interview for DSM-5⁵³. Subjects will undergo laboratory testing that includes liver function, electrolytes, blood chemistries, urine analysis, urine toxicology and a urine pregnancy test for women of child bearing age.

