After the 7-10 day washout period subjects will return to the lab to receive study medication prior to the alcohol challenge #2. Subjects will complete the same tests and interviews completed during the randomization visit (See appendix A for schedule of events). Based on the assessments at medication visit #2, subjects be discontinued for the following reasons: pregnancy, recreational drug use, evidence of non-compliance with study medication, suicidal thoughts or behavior, and use of a new medication that would make participation unsafe. Subjects will receive an 8-day supply of study medication and will be scheduled for the alcohol challenge #2.

Alcohol Challenge Trials 1 & 2: Subjects will return to the laboratory on day 8 of titration for each medication trial to complete the alcohol challenge. For safety reasons, subjects will be asked to arrange transportation plans (no driving) prior each of the alcohol challenge trials.

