Informed Consent	х				
Urine Drug Screen ^A	х	х	х	х	х
Locator Form	х				
Demographics	х				
Medical History	х				
Physical Exam	х				
MINI V 6.0	х				
Clinical Hematology and Chemistry BUN, Ca, CO2, Cl, Cr, G K, Na, Triglycerides, AST, ALT, GGT, Tbili	х				
Urinalysis	х				
COWAT, Digit Span, Spatial Span			Х		х
Vital Signs, weight, Blood Alcohol Level ^b	хх	х	x	х	х
ECG	х				
Prior and Concomitant Meds	х	х	Х	х	х
CIWA-AR	х	х	х	х	х
Eligibility Checklist	х				
Drug compliance/accountability			х		х
Urine Pregnancy Test	х	х	Х	х	х
Birth control assessment	х	х	Х	х	
AEs	х	х	Х	х	х
C-SSRS	х	х	Х	х	х
Dispense medication/placebo		х		х	
Brief Telephone Interview		Mid-week call 3-4 days after starting medication		Mid-week call 3-4 days after starting medication	
Treatment Referral					х
TLFB (28 day at baseline)	х	х	х	х	Х
VAS		х	Х	х	Х
OCDS		х	Х	х	Х
AUQ		х	х	х	х

- A) Test for opioids, cocaine, amphetamines, methamphetamine, tetrahydrocannabinol (THC), barbiturates, oxycodone, buprenorphine, methadone and benzodiazepines.
- B) if the baseline visit is split between two days, vitals, breathalyzer, and weight are to be taken at each visit.

16. Appendix B: Schedule of assessments during the alcohol challenge

	Observation	Self-admin Block1	Self-admin Block2
Assessment			
BAC	Every 10 minutes	Every 30 minutes	Every 30 minutes
vas vas	Every 10 minutes	Every 30 minutes	Every 30 minutes
AUQ		Every 30 minutes	Every 30 minutes

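### Exclusion item 8 in 7.2 omits the suicidal behavior on the C-SSRS that 6.1 says bars entry, and may also omit some active ideation

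*Combined protocol and SAP*

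**What the plan says.** Section 6.1 (Psychiatric risks) gives two suicidality exclusions. One uses the MINI: "Subjects with a MINI suicidality score greater than 8 (low risk) will be excluded". The other uses the C-SSRS: "Subjects who report any active suicidal thoughts or behavior as measured the C-SSRS will be excluded from participation". Neither is limited to a particular visit.

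Section 7.2, item 8, combines the two instruments in one entry: "Current risk of suicidality (MINI suicidality score greater than 8 (low risk) or Yes to the ideation question #4 of the C-SSRS". No other item in 7.2 mentions the C-SSRS or suicidal behavior.

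Section 9 (Medication Visit #2) includes suicidality among the reasons for discontinuation: "recreational drug use, evidence of non-compliance with study medication, suicidal thoughts or behavior". Appendix A schedules the C-SSRS at all five visits and marks the "Eligibility Checklist" at baseline only. The text of that checklist is not in the documents.

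**The concern.** The two sections agree on the MINI and differ on the C-SSRS. The wider rule stands in a risk narrative; the narrower one stands in the numbered list that defines who is excluded. A coordinator could reasonably treat that list as the working rule, because several other 6.1 exclusions do reappear in it. For example, "Treatment-seeking drinkers will be excluded from this study" in 6.1 becomes item 1; pregnancy becomes item 4, and medication that slows cardiac conduction becomes item 9.

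The stake is participant safety. Section 6.1 says that treatment with any anticonvulsant, including lacosamide, "must be considered to produce to an increased risk of suicidal thoughts and behaviors", and offers this screen as the way to limit that risk. If the checklist follows 7.2, the screen actually used is weaker than the one 6.1 promises.

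**Working it through.** No calculation applies, and the plan states no figure to reproduce. The check is a comparison of the two rules.

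**Step 1. The rules side by side.**

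| Part | 6.1 Psychiatric risks | 7.2 item 8 |
|---|---|---|
| MINI suicidality score | above 8 | above 8 |
| C-SSRS, thoughts | any active thoughts | Yes on ideation question #4 |
| C-SSRS, behavior | named | not named |

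Section 6.1 names two C-SSRS triggers (active thoughts; behavior). Item 8 names one (ideation question #4).

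**Step 2. Candidate profiles under each rule.**

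| Profile | 6.1 | 7.2 item 8 |
|---|---|---|
| MINI above 8 | excluded | excluded |
| MINI 8 or less, Yes on #4 | excluded, if #4 asks about active thoughts | excluded |
| MINI 8 or less, No on #4, suicidal behavior on the C-SSRS | excluded | not excluded |
| MINI 8 or less, No on #4, no behavior, positive on another ideation item | depends on whether that item measures active thoughts | not excluded |

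The third row needs no knowledge of the scale beyond what item 8 itself says: a question about ideation is not a question about behavior. If the word *active* in 6.1 is taken to qualify behavior as well as thoughts, this row covers current behavior only. The fourth row cannot be settled, because the documents give the content neither of question #4 nor of the other ideation items.

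**Step 3. Does anything else in 7.2 close the gap?** Item 3 covers listed diagnoses, including current major depression and bipolar disorder. Item 7 covers conditions for which further alcohol exposure is contraindicated. Either may catch some of the same people, but neither refers to the C-SSRS or to suicidal behavior. The opening words of item 8 are broad, but the parenthesis that follows defines them.

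**Step 4. How many people?** This cannot be computed. The documents do not say what the MINI score counts. If suicidal behavior already lifts that score above 8, the gap for behavior may be close to nil. If it does not, the gap is everyone with behavior on the C-SSRS, a MINI score of 8 or less and No on #4. The 6.1 figures for antiepileptic drugs (0.43% against 0.24% on placebo, a difference of 0.43 − 0.24 = 0.19 percentage points) show why the screen matters. They do not measure this gap.

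**The case against.** The strongest reply is that nobody need be enrolled wrongly. Section 6.1 is mandatory, and 7.2 says that meeting a listed criterion excludes a person, not that nothing else does. Staff must already apply at least one exclusion from outside the list: Section 9 excludes those who purposefully stopped drinking and reached 7 days of abstinence, which 7.2 does not mention. This stands. Both texts can be obeyed together by applying the stricter one, so item 8 is incomplete rather than in outright contradiction with 6.1.

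The safeguards are also real: "Assessment and scoring of suicide rating scales will be conducted in real-time while the subject is present", by trained clinical staff, with a safety plan for anyone at risk. There is a call on day 3 of titration and a 24/7 medical contact. These lower the chance of harm but do not make the two rules agree.

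Three stronger readings are tempting and are not supported:

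- **Item 8 certainly drops other active ideation.** Without the content of the C-SSRS items, question #4 could be the sponsor's working form of active suicidal thoughts. Only the omission of behavior is shown by the text.
- **The protocol admits people whom it says it excludes.** That requires staff to screen from 7.2 alone, or from a checklist that copies it, and requires the MINI not to catch the same people. None of this is documented.
- **The Medication Visit #2 rule proves that the wider entry rule was intended.** It fits that reading, but it is a discontinuation rule applied after Trial 1, when a participant may already have taken lacosamide. It does not fix the entry threshold.

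**Conclusion.** The point holds in a limited form. Item 8 does not carry over the C-SSRS exclusion stated in 6.1: it omits suicidal behavior, and it may omit other active ideation. The first part rests on the wording alone. The second depends on instrument content that the documents do not give.

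The practical consequence is conditional. A candidate barred by 6.1 could be enrolled only if screening is done from 7.2 or from a checklist copied from it, and how many that would be is unknown. Severity is minor to should-fix. It is worth correcting because the item governs a safety screen and one of the two texts has to change for them to agree. Endpoints, analysis, sample size and error rates are unaffected.

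**What to change.** Reword item 8 to the scope of 6.1, for example: *Current risk of suicidality: MINI suicidality score above 8, or any active suicidal thoughts or behavior on the C-SSRS within [look-back period].* The investigator should choose a look-back consistent with current risk and write it into the item, since neither section gives one. Without it, the item could exclude people for remote lifetime behavior, which may go further than 6.1 intends. Put the same wording on the eligibility checklist, and confirm what that checklist says now.

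If the sponsor does intend question #4 as the threshold, the alternative is to amend 6.1 to say so and justify leaving behavior out.

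The cost is a wording amendment. The MINI and C-SSRS are already given at baseline, so no assessment is added; the downside is possibly a few more screen failures. Stating that the same rule applies to the C-SSRS at randomization and Trial 1 would be an optional clarification, which this mismatch does not require.
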